Screening/Washout Visits	
Subjects with an ophthalmic history of increased IOP (≥ 22mmHg and ≤ 30 mmHg) will be selected for study participation and be screened for study eligibility.
 
After Screening, eligible subjects, if currently being treated with glaucoma medications, will be required to washout and refrain from administration of any glaucoma drugs for at least 28 days and no more than 35 days prior to the Qualification Visit. The washout subjects will be brought back at approximately two weeks after starting the washout period for an IOP safety check. In the judgement of the investigator, if there is any risk to the eye(s) of the subject, or if the mean IOP in either eye during washout is >30mmHg, then an appropriate rescue or prior medication will be administered, and the subject will be considered a screen failure. Adverse events occurring during the washout period will also be assessed at this visit.
 
Subjects not previously treated with any glaucoma drugs will not require a washout period and may return the following day or up to 35 days later for their Qualification/Baseline Visit.

Qualification/Baseline Visit	
After the washout, where applicable, a Qualification Visit will occur before dosing on Day 1.
 
At the Qualification Visit, IOP eligibility will be determined with [REDACTED] at 8AM, 10AM, and 4PM (mean IOP at 8AM must be ≥ 22mmHg and ≤ 30mmHg, and ≥ 19 mmHg at 10AM and 4PM). IOP will be measured twice in both eyes at each timepoint and the mean value will be used in eligibility assessments. All IOP measurements have a window of ± 15 minutes with at least 2 hours between the 8AM and 10AM assessments.
 
The eye with the higher IOP at the Qualification Visit at 8AM is designated as the study eye for the primary endpoint efficacy analysis. In the case where both eyes have the same IOP, the study eye will be the RIGHT eye. ALL TREATMENTS WILL BE ADMINISTERED TO BOTH EYES (OU).
 
If the subject meets all eligibility criteria, then the Qualification Visit is the Baseline Visit. The subject will then be randomized into the study.
 
The first dose of study medication will be taken at 8PM to 10PM on the Baseline Visit (Day 1).

Treatment-study Visits	
Treatment-study visits will occur twice - on Day 8 ± 1 Day and Day 15 ± 1 Day. IOP evaluations will be performed at 8AM,

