5. SUBJECT INCLUSION AND EXCLUSION CRITERIA

Subjects may qualify in either eye. The eye with the higher IOP at the Qualification/Baseline Visit at 8AM is designated as the study eye. In the case where both eyes have the same IOP, the study eye will be the RIGHT eye. See Section 9 for more information on statistical analysis. ALL TREATMENTS WILL BE ADMINISTERED TO BOTH EYES (OU).

5.1. *Subject inclusion criteria*

1. 18 years of age or greater.
2. Diagnosis of OAG or OHT. The diagnosis of OHT must be in BOTH eyes. For OAG it can be in either eye and OHT in the fellow eye. A reported history of untreated OHT with IOP ≥ 22 mmHg and ≤ 30 mmHg is preferred.
3. Untreated or treated OAG/OHT with 2 or fewer ocular hypotensive medications.
4. Untreated (post-washout) mean IOP ≥ 22 mmHg and ≤ 30 mmHg in the study eye at the Qualification Visit (8AM).
5. Corrected visual acuity in each eye $+1.0$ logMAR or better by Early Treatment Diabetic Retinopathy Study (ETDRS) in each eye (equivalent to 20/200 or better).
6. Otherwise healthy and well controlled subjects.
7. Able and willing to give signed informed consent and follow study instructions.
8. Able to self-administer study medication or to have study medication administered by a caregiver throughout the study period.

5.2 *Subject exclusion criteria*

Excluded from the study will be individuals with the following characteristics in either eye:

Ophthalmic:

1. Closed or very narrow angles (Grade 0-1, Shaffer¹) or angles that the investigator judges as occludable and/or with evidence of peripheral anterior synechiae (PAS) ≥ 180 degrees by gonioscopy within 6 months prior to Screening Visit in either eye.
2. Glaucoma: pseudo-exfoliation or pigment dispersion component, history of angle closure, or narrow angles. Note: Previous laser peripheral iridotomy is NOT allowed.
3. Known hypersensitivity to any α -adrenoceptor antagonists.
4. Previous laser and/or non-laser glaucoma surgery or procedure in either eye.
5. Refractive surgery in either eye (i.e. radial keratotomy, PRK, LASIK, corneal cross linking).
6. Ocular trauma in either eye within the 6 months prior to Screening, or ocular surgery or non-refractive laser treatment within the 3 months prior to Screening.
7. Recent or current evidence of ocular infection or inflammation in either eye. Current evidence of clinically significant blepharitis, conjunctivitis, or a history of herpes simplex or herpes zoster keratitis at Screening in either eye.

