7.2.2. Washout Period

After Screening, study participants will be required to refrain from administration of any glaucoma drugs for at least 28 days and no more than 35 days prior to the Qualification/Baseline Visit. The washout subjects will be brought back in approximately two weeks after the Screening Visit for an IOP safety check. In the judgement of the investigator, if there is any risk to the eye(s) of the subject, or if the mean IOP in either eye is >30 mmHg, then an appropriate rescue or prior medication will be administered, and the subject will be considered a screen failure. Adverse events occurring during the washout period and a review of concomitant medications will also be assessed at this visit.

Unmedicated subjects who meet the inclusion/exclusion criteria after screening do not have a washout period. These subjects may return the following day or up to 35 days later for their Qualification/Baseline Visit.

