7.2.3. Qualification Visit/Baseline (Day 1)

At the Qualification/Baseline Visit, the subject will be asked how do his/her eyes feel, and if there have been any changes in their medical condition, or concomitant medications since their last visit. Any adverse changes in the condition of the subject at this visit are recorded in the Medical/Ophthalmic History CRF.

At the Qualification/Baseline Visit:

- Females of childbearing potential will take a urine pregnancy test at 8AM.
- Review of concomitant medications at 8AM.
- IOP measurements using a [REDACTED] at the Baseline visit and both Treatment-study visits will be done at 8AM, 10AM and 4PM. All IOP measurements have a window of ± 15 minutes with at least 2 hours between the 8AM and 10AM assessments. IOP will be measured twice in both eyes at each timepoint. The mean value at each timepoint for the study eye will be used in efficacy assessments. If the difference in the two IOP measurements is >5 mmHg, a third measurement will be obtained, and the three values averaged.
- Pupil diameter, using a [REDACTED], near visual acuity using a standard chart held at 14 inches and distance visual acuity with ETDRS are measured at 8AM.
- Resting HR and BP are measured at 8AM and 4PM. Blood pressure, using the same arm, same cuff size appropriate for arm circumference throughout the study, and heart rate should be measured after at least 3 minutes rest in the sitting position. If HR or BP are outside the normal range (see Exclusion Criteria – Systemic #7 and #8), they may be repeated only once following at least a 5 minute rest period in the sitting position.
- Eye redness (conjunctival hyperemia) visually checked at 8AM, 10AM and 4PM using [REDACTED]
- Adverse events will be reviewed at each timepoint.

To continue in the study, the subject must have a mean IOP ≥ 22 mmHg at 8AM and ≥ 19 mmHg at 10AM and 4PM in the study eye **after the washout period** (if required) at the Qualification Visit (8AM).

Subjects may qualify in either eye. The eye with the higher IOP at the Qualification Visit at 8AM is designated as the study eye for the efficacy endpoints. In the case where both eyes have the same IOP, the study eye will be the RIGHT eye. See Section 9 for more information on statistical analysis. ALL TREATMENTS WILL BE ADMINISTERED TO BOTH EYES (O.U.).

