7.2.4. Study Day 8 ± 1 Day

On Study Day 8, the subject should bring their used dropper bottles with any unused medications with them for purposes of drug accountability. At the end of the Study Day 8 Visit the study medication box will be re-dispensed with the unopened medication.

The subjects will be asked if they had any problems with their eyes from the last visit, and if there have been any changes in their medical condition, or concomitant medications since their last visit. ***Any changes in the condition of the subject are recorded as an adverse event.***

In addition, on Study Day 8:

- Review of concomitant medications at 8AM.
- IOP measurements will be done at 8AM, 10AM and 4PM. All IOP measurements have a window of ± 15 minutes with at least 2 hours between the 8AM and 10AM assessments. IOP will be measured twice in both eyes at each timepoint. The mean value at each timepoint for the study eye will be used in efficacy assessments. If the difference in the two IOP measurements is > 5 mmHg, a third measurement will be obtained, and the three values averaged.
- Pupil diameter, near and distance visual acuity, resting heart rate and blood pressure are measured at 8AM. Blood pressure, using the same arm, same cuff size appropriate for arm circumference throughout the study, and heart rate should be measured after at least 3 minutes rest in the sitting position. If HR or BP are outside the normal range (see Exclusion Criteria – Systemic #7 and #8), they may be repeated only once following at least a 5 minute rest period in the sitting position.
- Eye redness (conjunctival hyperemia) visually checked at each timepoint using [REDACTED] scale.
- Adverse Events will be reviewed at each timepoint.

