7.2.5. Study Day 15 \pm 1 Day

On Study Day 15, the subject should bring their used dropper bottles and any unused medications with them for purposes of drug accountability.

The subjects will be asked if they had any problems with their eyes from the last visit, and if there have been any changes in their medical condition, or concomitant medications since their last visit. ***Any changes in the condition of the subject are recorded as an adverse event.***

In addition, on Study Day 15:

- Review of concomitant medications and a urine pregnancy test at 8AM.
- IOP measurements will be done at 8AM, 10AM and 4PM. All IOP measurements have a window of ± 15 minutes with at least 2 hours between the 8AM and 10AM assessments. IOP will be measured twice in both eyes at each timepoint. The mean value at each timepoint for the study eye will be used in efficacy assessments. If the difference in the two IOP measurements is >5 mmHg, a third measurement will be obtained, and the three values averaged.
- Pupil diameter, near and distance visual acuity, resting heart rate and blood pressure are measured at 8AM. Blood pressure, using the same arm, same cuff size appropriate for arm circumference throughout the study, and heart rate should be measured after at least 3 minutes rest in the sitting position. If HR or BP are outside the normal range (see

Exclusion Criteria – Systemic #7 and #8), they may be repeated only once following at least a 5 minute rest period in the sitting position.

- Eye redness (conjunctival hyperemia) visually checked at each timepoint [REDACTED]
- Adverse Events will be reviewed at each timepoint.
- Distance and near visual acuity, pupil diameter, and a complete ophthalmic examination, including biomicroscopy will also be performed at 4 PM.

Subjects completing their Day 15 Visit should be instructed **not** to resume their original glaucoma medication(s) until after completion of the Day 22 Follow-up phone call.

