7.2.6. Follow-up Visit (Day 16)

The subjects will be asked if they had any problems with their eyes from the last visit, and if there have been any changes in their medical condition, or concomitant medications since their last visit. *Any changes in the condition of the subject are recorded as an adverse event.*

In addition, on Study Day 16:

- Review of concomitant medications at 8AM.
- IOP is measured twice in the study eye at 8AM \pm 15 minutes and the two values are averaged. If the difference in the two IOP measurements is >5 mm Hg, a third measurement is obtained, and the three values are averaged.
- Pupil diameter, near and distance visual acuity, resting heart rate and blood pressure are measured at 8AM. Blood pressure, using the same arm, same cuff size appropriate for arm circumference throughout the study, and heart rate should be measured after at least 3 minutes rest in the sitting position. If HR or BP are outside the normal range (see Exclusion Criteria – Systemic #7 and #8), they may be repeated only once following at least a 5 minute rest period in the sitting position.
- Eye redness (conjunctival hyperemia) visually checked at each timepoint using [REDACTED]
- Adverse Events will be reviewed at 8AM.

Subjects completing their Day 16 Visit should be reminded **not** to resume their original glaucoma medication(s) until after completion of the Day 22 Follow-up phone call.

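### The 30 mmHg limit that mandates rescue in washout is applied only at 8AM at Qualification, and the instruction to stay off glaucoma medication until the Day 22 call has no stated exception

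*Protocol*

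**What the plan says.** **Washout.** Subjects who stop glaucoma drugs are "brought back in approximately two weeks after the Screening Visit for an IOP safety check". The rule at that visit is "if the mean IOP in either eye is >30 mmHg, then an appropriate rescue or prior medication will be administered" (Protocol 7.2.2), and the subject is then a screen failure. Investigator-judged risk to the eye has the same consequence. The Study Summary repeats the rule and confines it to washout. Previously untreated subjects have no washout and no such check.

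**Qualification.** The Study Summary states: "mean IOP at 8AM must be ≥ 22mmHg and ≤ 30mmHg, and ≥ 19 mmHg at 10AM and 4PM". Inclusion criterion 4 (Protocol 5.1) has the 8AM range alone: "Untreated (post-washout) mean IOP ≥ 22 mmHg and ≤ 30 mmHg in the study eye at the Qualification Visit (8AM". Protocol 7.2.3 gives floors without any ceiling: "the subject must have a mean IOP ≥ 22 mmHg at 8AM and ≥ 19 mmHg at 10AM and 4PM in the study eye". The same section requires all inclusion criteria to be met, so the 8AM ceiling still binds. No upper limit is written for 10AM or 4PM.

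**After randomisation.** IOP is read at 8AM, 10AM and 4PM on Days 8 and 15 (7.2.4, 7.2.5) and at 8AM on Day 16 (7.2.6). The only visible numeric trigger in these sections is a gap of more than 5 mmHg between paired readings, which prompts a third reading. On Day 15 subjects are instructed not "to resume their original glaucoma medication(s) until after completion of the Day 22 Follow-up phone call". Section 7.2.6 repeats this on Day 16. The Day 22 contact is a telephone call (7.2.7).

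**The concern.** The sponsor chose 30 mmHg as the pressure above which an unmedicated subject in washout must be treated and may not continue. Two later rules do not carry that limit forward.

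First, at Qualification a subject can exceed 30 mmHg at 10AM or 4PM, satisfy every written IOP criterion and be randomised, possibly to vehicle.

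Second, after the Day 15 4PM reading the primary endpoint is complete, and after Day 16 no IOP reading remains. Staying off medication from Day 16 to Day 22 therefore protects no efficacy measurement. Yet the instruction to wait is unconditional as written, including for a subject whose pressure on Day 15 or 16 was above the washout limit.

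What is at stake is subject safety and consistent handling across about five sites. Bias in the primary endpoint is a minor matter here.

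**Working it through.** This is mainly a comparison of text; the arithmetic is short. The plan's stated length of participation reproduces: washout of 28 to 35 days, plus 22 − 1 = 21 days from Day 1 to the Day 22 call, gives 49 to 56 days, or 7 to 8 weeks. That is the planned time off therapy for a washed-out placebo subject and does not result from the gap.

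**1. The IOP limits side by side**

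| Stage | Upper limit in the visible text | Stated consequence |
|---|---|---|
| Washout check | 30 mmHg, either eye | Rescue or prior medication, and screen failure |
| Qualification 8AM | 30 mmHg, study eye | Ineligible |
| Qualification 10AM and 4PM | None (floor of 19 mmHg) | None |
| Days 8, 15 and 16 | None visible | None visible |

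The study eye is the one with the higher 8AM pressure, so the 8AM ceiling also holds the fellow eye at or below 30 mmHg at that hour. Neither eye is capped at 10AM or 4PM.

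**2. A case that passes.** Take 29 mmHg at 8AM, 27 at 10AM and 32 at 4PM. The checks are 22 ≤ 29 ≤ 30, 27 ≥ 19 and 32 ≥ 19. All are met. With 1:1 allocation the chance of placebo is 50%.

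**3. Time left without a stated limit**
- From the washout check (about day 14) to Day 22: (28 − 14) + 21 = 35 days, to (35 − 14) + 21 = 42 days. This span holds ten scheduled IOP timepoints (three each on Days 1, 8 and 15, one on Day 16), so subjects are observed. The only stated upper limit in it is the 8AM ceiling on Day 1.
- From a high reading to the call: 22 − 15 = 7 days from Day 15, and 22 − 16 = 6 days from Day 16. Under 7.2.9 the later contacts move with a shifted Day 15 visit, so these intervals do not change.

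**4. How often? Illustration only.** The documents give no distribution of single IOP readings. The planning SD of 3.0 is for change in mean diurnal IOP. Assume a later same-day reading is Normal with mean b − f and SD s, where b is the 8AM value and f the fall during the day. Then P(>30) = P(Z > (30 − b + f)/s). I take f = 3 (the gap between the 22 and 19 floors) or 0, and s = 2 or 3.

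| b | f = 3, s = 2 | f = 3, s = 3 | f = 0, s = 2 | f = 0, s = 3 |
|---|---|---|---|---|
| 29 | 2.3% | 9.1% | 30.9% | 36.9% |
| 24 | <0.01% | 0.13% | 0.13% | 2.3% |

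Averaged over an assumed baseline, either Normal(24, 2) truncated to 22–30 or uniform on 22–30, the expected number among 40 subjects runs from 0.03 (truncated Normal, f = 3, s = 2) to 5.97 (uniform, f = 0, s = 3) for one later timepoint. That range is about 200-fold. It shows that the event is possible and that its frequency is unknown.

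**5. Why Day 8 differs.** A subject who stops study drug at the Day 8 visit has taken the doses of Days 1 to 7, that is 7. The FAS requires at least 11 (Protocol 9.2, SAP 7.1.1), so that subject leaves the primary analysis. Rescue after the Day 15 4PM reading leaves the primary endpoint untouched.

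**The case against.** The strongest reply is that real protection exists:
- Ophthalmic exclusion 9 keeps out eyes too damaged for a month's washout.
- The investigator or Medical Monitor may withdraw a subject (4.9), and study drug may be stopped in the subject's interest (4.9.1).
- Subjects who stop because of an adverse event must receive appropriate care (4.9.4).
- Unscheduled visits are open-ended (7.2.8).
- At the on-treatment and follow-up visits, "Any changes in the condition of the subject are recorded as an adverse event". Adverse events may be treated as the investigator sees fit (8.3.2), and the action codes in 8.3.1 foresee a new prescription drug.

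This stands. A reader might infer that the protocol forbids treating a high pressure after randomisation, or leaves subjects unprotected; the documents do not support that. What remains is that none of these routes carries a pressure limit. They also sit beside a ban on other ocular medication during the study (6.2) and the instruction to wait for Day 22.

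A reader might also infer that no action level exists anywhere for Days 8 to 16. That cannot be established: Table 1 is missing from the protocol text and redacted in the SAP, and the IOP procedure cells in Protocol 7.2 and SAP Table 2 are redacted. The Qualification gap does not depend on this material, because the criteria are visible in full.

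It can further be said that 30 mmHg in washout simply mirrors the eligibility ceiling, and that nothing makes it the treatment level for a randomised subject. That is fair, and it is why a mandatory 30 mmHg stopping rule at Day 8 would go too far: it would remove high-pressure subjects from the FAS, plausibly more on placebo, and make exclusion depend on outcome.

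Finally, the Day 16 wording "IOP is measured twice in the study eye at 8AM" may be a slip, since Protocol 4.1 says IOP is measured in both eyes and analyses Day 16 by fellow eye.

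**Conclusion.** The point holds in a limited form. On visible text, a subject above the sponsor's own washout rescue level at 10AM or 4PM meets the IOP criteria and can be randomised, with a 50% chance of placebo. On visible text, the instruction at Days 15 and 16 has no stated exception, which leaves 6 to 7 days in which earlier treatment depends on each investigator's judgement without a common limit.

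The number of subjects affected is unknown and may be small. The 0.03 to 5.97 of 40 above rests entirely on assumed baselines, spreads and falls. The conclusion rests on the wording and not on that range.

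It does not extend to a finding that the trial lacks safety provisions, that a Day 8 action level is definitely absent, or that the primary endpoint is materially biased. The changes are worth making because they are cheap and nearly all concern readings already scheduled.

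**What to change.** 1. **Qualification.** In the Study Summary, inclusion criterion 4 and Protocol 7.2.3, apply the ≤30 mmHg ceiling at 10AM and 4PM in either eye, as well as at 8AM. Cost: a few more screen failures, number unknown.

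2. **Days 15 and 16.** In 7.2.5 and 7.2.6, state that a subject with a confirmed mean IOP >30 mmHg in either eye after the Day 15 4PM reading or on Day 16, or judged at risk by the investigator, may resume prior or rescue medication at once without waiting for Day 22. Make clear in 7.2.6 that both eyes are read. Cost: possible loss of the Day 16 secondary IOP reading for a subject treated on Day 15, some confounding of the Day 22 safety call, and one fellow-eye reading if 7.2.6 is now taken literally. The primary endpoint is unaffected.

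3. **Day 8.** At most, state in 7.2.4 that a confirmed high reading, at a level set by the sponsor's clinicians, prompts Medical Monitor review and that rescue is permitted. Keep rescued subjects in the All Randomized analysis, because those who stop drug at Day 8 leave the FAS. Cost: some loss from the primary analysis set, less with a higher level.

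If Table 1 or the redacted procedure text already holds an action level, repeat it in these sections.

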7.2.3. Qualification Visit/Baseline (Day 1)

At the Qualification/Baseline Visit, the subject will be asked how do his/her eyes feel, and if there have been any changes in their medical condition, or concomitant medications since their last visit. Any adverse changes in the condition of the subject at this visit are recorded in the Medical/Ophthalmic History CRF.

At the Qualification/Baseline Visit:

- Females of childbearing potential will take a urine pregnancy test at 8AM.
- Review of concomitant medications at 8AM.
- IOP measurements using a [REDACTED] at the Baseline visit and both Treatment-study visits will be done at 8AM, 10AM and 4PM. All IOP measurements have a window of ± 15 minutes with at least 2 hours between the 8AM and 10AM assessments. IOP will be measured twice in both eyes at each timepoint. The mean value at each timepoint for the study eye will be used in efficacy assessments. If the difference in the two IOP measurements is >5 mmHg, a third measurement will be obtained, and the three values averaged.
- Pupil diameter, using a [REDACTED], near visual acuity using a standard chart held at 14 inches and distance visual acuity with ETDRS are measured at 8AM.
- Resting HR and BP are measured at 8AM and 4PM. Blood pressure, using the same arm, same cuff size appropriate for arm circumference throughout the study, and heart rate should be measured after at least 3 minutes rest in the sitting position. If HR or BP are outside the normal range (see Exclusion Criteria – Systemic #7 and #8), they may be repeated only once following at least a 5 minute rest period in the sitting position.
- Eye redness (conjunctival hyperemia) visually checked at 8AM, 10AM and 4PM using [REDACTED]
- Adverse events will be reviewed at each timepoint.

To continue in the study, the subject must have a mean IOP ≥ 22 mmHg at 8AM and ≥ 19 mmHg at 10AM and 4PM in the study eye **after the washout period** (if required) at the Qualification Visit (8AM).

Subjects may qualify in either eye. The eye with the higher IOP at the Qualification Visit at 8AM is designated as the study eye for the efficacy endpoints. In the case where both eyes have the same IOP, the study eye will be the RIGHT eye. See Section 9 for more information on statistical analysis. ALL TREATMENTS WILL BE ADMINISTERED TO BOTH EYES (O.U.).

If the subject meets all of the inclusion criteria and none of the exclusion criteria, including all three timepoint IOP measurements, this qualification visit becomes the Baseline Visit, a subject number is assigned, and he/she is randomized into the study.

Site personnel will demonstrate the proper instillation technique to the subject at the Qualification/Baseline Visit (Day 1) and the subject will self-administer a dose of artificial tears at the study site, instilling 1 drop in each eye from the unit-dose bottle (Note: if a drop is not instilled into the eye, the subject should wait approximately 10-15 seconds and administer a second drop). The subject should be in a seated position and should tilt his or her head backward for administration of the study medication. The bottle of study medication should be held at an almost vertical position above the eye while the lower eyelid is pulled down gently, and 1 drop is placed into the conjunctival cul-de-sac. The tip of the bottle should not touch the eye. After a drop is instilled in each eye, the subject should keep the eyes gently closed for approximately 30 seconds. After successful instillation of the drop in each eye, the subject should carefully empty any remaining contents as directed.

The subject is given their study medication dropper bottles, and with instructions when to administer the eye drop (8PM to 10PM), and when to return to the clinic.

Each subsequent evening of dosing, the subject will administer one drop to each eye from a single new unit-dose bottle and close the eyes gently for 30 seconds, then empty the remaining contents and store the opened bottle in the baggie provided and place it in the medication box for return to the study site at the Day 8 Visit. Each subsequent evening of dosing (approximately 24 hours between doses), the subject will follow the same procedures. At the Day 8 visit the medication box, complete with opened bottles and any unopened study medication will be returned to the study site where the baggies of opened medication will be removed, and the study medication box will be re-dispensed with the unopened medication. During the second week of treatment, subjects will continue to administer one drop of study medication to each eye every night using a new bottle for each dose, then emptying the remaining contents of that bottle and storing the opened bottles in the baggies and placing them back in the box to return to the study site at the Day 15 Visit. The Day 15 visit will be the last day of study treatment; no further study medication will be dispensed at this visit.

The subject should be instructed to contact the investigator should adverse events of concern occur (e.g., shortness of breath, fainting, etc.). If the event is life-threatening, then the subject should go to the emergency room.

